## 2.3 Stopping Rules

An independent Data and Safety Monitoring Board (DSMB), conducted ongoing review of blinded and unblinded data, including safety and confirmed cases of COVID-19 at data review meetings.

At each meeting, the DSMB reviewed the available data and made a recommendation to the Sponsor to continue, modify, or discontinue study enrollment (while the study was enrolling). In addition to the ongoing review of safety data, the DSMB also reviewed available severe

COVID-19 case data to determine the risk of vaccine-associated enhanced respiratory disease (VAERD).

## 2.4 Blinding

The study vaccines were administered in an observer-blind fashion.

In order to maintain an observer-blind design, investigators, site staff, participants, and CRO staff with oversight of study conduct remained blinded to vaccine assignments for the study duration. The Sponsor and Arcturus' representatives with direct safety oversight of the study remained blinded to individual participant vaccine assignments until the time that the study is fully unblinded. The Switchover/Further Study Vaccine occurred in a blinded fashion and participants and blinded site and Sponsor personnel remained blinded to treatment assignment until End of Study (EOS).

Additional members of the Sponsor team that were not involved in direct oversight of the study may have received unblinded study data but did not share any unblinded information with the Sponsor team overseeing the study. Sponsor staff and other persons that became unblinded at the various data analysis time points were specified in a written unblinding plan prior to unblinding occurring.

Specific considerations for sponsor personnel unblinding at the time of SAP writing are described in Section 2.5 on interim analyses (IA).

A small team of individuals at Arcturus involved in the authorship of the 6-month and final SAPs was included in the list of individuals who had access to the unblinded data at the participant level through Ministry of Health (MOH) analyses (2 analyses). The first analysis was performed on the safety and immunogenicity data from participants in the Phase 1/2/3a study. The second analysis was performed on the safety, immunogenicity, and efficacy data from participants in the Phase 1/2/3a/3b portions of the study.

This was not thought to influence the development of the 6-month and final SAP which is largely streamlining the original analyses and stating specifics for the final analysis of data (more details described on Section 2.5).

No analysis of Phase 3c data was performed in the IAs, and this study part is blinded in this final analysis SAP development.

## 2.5 Interim Analyses

Per Vietnam MOH request, unblinded safety analysis including data through Day 92 and immunogenicity analysis including data through Day 57 in Phase 1/2/3a participants were performed. The immunogenicity analysis included all data to support the evaluation of the immunogenicity objectives in Phase 1/2/3a. This first analysis was used to support the emergency use authorization (EUA) in Vietnam.

Per Vietnam MOH request, the unblinded Phase 3b safety and efficacy analyses were performed when all participants in Phase 3b that were evaluable for the primary efficacy endpoint had reached Day 92 and all potential COVID-19 events in these participants up to Day 92 had been adjudicated by the blinded Independent Adjudication Committee. This second analysis was also used to support the EUA in Vietnam.

An additional 6-month safety analysis was performed when all participants in Phase 1/2/3a/3b had at minimum of 6-month safety follow-up. The 6-month safety analysis also included all analyses of efficacy and immunogenicity previously conducted per Vietnam MOH requests, as well as analyses of results generated by using additional immunogenicity assays. In addition, the 6-month analysis was the subject of the interim CSR and provided updated safety (Phase 1/2/3a/3b) and immunogenicity (Phase 1/2/3a) data. The 6-month analysis is a CDISC-compliant implementation of previous MOH analyses with updated safety data including up to 6-month follow-up and additional immunogenicity analysis to support the ex-Vietnam regulatory submissions. Version 1.0 of the SAP for this analysis was finalized and signed on 02 December 2022. In order to clarify analysis and align with recommendations provided during an European Medicines Agency pre-submission interaction discussion on 31 January 2023, the SAP was revised on 10 March 2023 after extraction of the data for the analyses, which occurred on 12 January 2023. The data cut point for immunogenicity and safety for this analysis was 12 January 2023 when all participants in Phases 1, 2, 3a, and 3b had been followed up for at least 6 months after the 2nd vaccination (or had terminated early). The data cut point for VE remained the same (i.e., Day 92 visit) as that for the earlier analysis, ie, 30 March 2022. Immunogenicity analyses were presented up to Day 120, which was the last timepoint at which immunogenicity is assessed prior to the EOS (Day 394). Safety data were presented up to 6 months after the 2nd dose.

Since not all associated data were fully cleaned, these analyses are still considered as interim. However no multiplicity adjustments will be made for these and subsequent final analyses, as the final analyses are reflective of the MOH and 6-month analyses using the same set of endpoint data.

#### Phase 1/2/3a

The primary immunogenicity analysis for Phase 1/2/3a was performed after all participants in this cohort reached the Day 57 timepoint.

The primary Phase 1/2/3a analysis of safety was performed when all participants in this cohort reached Day 92.

First interim analysis of safety data through at least Day 57 were performed for Phase 1/2/3a at the time of analysis of the primary immunogenicity endpoint of Phase 1/2/3a to support application for EUA in Vietnam.

Safety data before Day 57 and efficacy data before Day 92 were entered into the EDC, verified and validated where possible prior to the data extractions for the interim analyses for EUA.

Randomization was opened for the subgroup of participants who were further randomized to receive ARCT-154 or placebo at Day 92, in order to conduct Day 120 analyses to evaluate safety and immunogenicity following the third dose. Sponsor and CRO staff responsible for day-to-day conduct of the study will remain blinded until the final unblinding of data at the end of study occurs in order that safety assessments can continue in an unbiased fashion.

### Phase 3b

The primary Phase 3b analysis of safety and efficacy were performed when all participants in Phase 3b that were evaluable for the primary efficacy analysis had reached Day 92 and all COVID-19 events in these participants up to Day 92 had been adjudicated by the blinded Independent Adjudication Committee.

Subsequent analyses of safety would be exploratory. However, Sponsor and CRO staff responsible for day-to-day conduct of the study would remain blinded until the final unblinding of data at the end of study occurs in order that safety assessments can continue in an unbiased fashion. SAP Part 1 and Part 2 were finalized prior to the second of two interim analyses performed by Vinbiocare in April 2022 although the SAPs were finalized and the analyses were intended for execution by another vendor, Biophics. The plan was partially implemented by Vinbiocare due to the severe COVID-19 outbreak in Vietnam and the interest in a faster and focused review of the data.

The analyses that were therefore performed by Vinbiocare included the following features:

- They were requested by the Vietnam MOH as part of the ongoing review of the ARCT-154 program for consideration of an Emergency Use Authorization.
- The first analysis performed by Vinbiocare focused on the safety and immunogenicity data from participants in the Phase 1/2/3a study.
- A small team of individuals at Vinbiocare and Vietstar were unblinded for this analysis. These individuals did not contribute to the finalization of both SAP Part 1 and Part 2.
- The second analysis performed by Vinbiocare focused on the safety, immunogenicity, and efficacy data from participants in the Phase 1/2/3a/3b portions of the study. This analysis was also performed in collaboration with Vietstar. The analysis was aligned with, but did not follow, all elements of SAP Part 2.

### 3 STUDY ENDPOINTS

Study endpoints corresponding to protocol objectives assessed as part of the final analysis are briefly described in Table 1, Table 2, Table 3, and Table 4 and are covered in more details within analysis methods in Table 6, Table 7, and Table 8.

## 4 ANALYSIS SETS

### 4.1 Analysis Set Definitions

- **All Screened Participants:** Includes all participants who signed informed consent form. This analysis sets are defined for each Phase of the study as follows:
  - Phase 1/2/3a: this pools data from Phase 1, 2 and 3a participants
  - Phase 3b
  - Phase 3c
  - Pooled: this pools data from Phase 1, 2, 3a and 3b participants
- **Randomized Set (RS):** Includes all participants who are randomly assigned in the study regardless of the participants' vaccination status in the study. Participants will be analyzed according to the vaccine to which the participant was randomly assigned. RS are defined for each Phase of the study as follows:
  - Phase 1/2/3a RS: this pools data from Phase 1, 2 and 3a participants
  - Phase 1 RS
  - Phase 2/3a RS
  - Phase 3b RS
  - Phase 3c RS
  - Pooled RS: this pools data from Phase 1, 2, 3a and 3b participants

Participants who are entered into the unblinded part of IVRS will receive a random ID (randomID). Participants who received a randomID will be entered into the blinded part of the IVRS to receive the treatment assignment. Participants with an assigned randomID but without assigned treatment in the IVRS system will not be considered as randomized.

- **Intent-to-Treat (ITT) Analysis Set:** Includes all participants who receive any dose of study vaccine (ARCT-154 or placebo or ChAdOx1). Participants will be analyzed according to the vaccine to which the participant was randomly assigned. ITT are defined for each Phase of the study as follows:
  - Phase 3b ITT
  - Phase 3c ITT
  - Phase 1/2/3a ITT: this pools data from Phase 1, 2 and 3a participants and will include evaluations up to Day 92 only
  - Pooled ITT: this pools data from Phases 1/2/3a/3b and will include evaluations up to Day 92 only

- **Modified Intent-to-Treat (mITT) Analysis Set:** Includes all participants who received all protocol-required doses of study vaccine (ARCT-154 or placebo or ChAdOx1) up to the evaluation timepoint concerned, and who have no evidence of SARS-CoV-2 infection (no positive RT-PCR or other COVID-19 test or seropositivity for anti-nucleocapsid antibody) on Day 1 or up to 7 days after the 2nd study vaccination. The mITT analysis set will be analyzed according to vaccine assigned. The mITT analysis sets are defined for:
  - Phase 3b mITT
  - Phase 1/2/3a mITT
  - Phase 3c mITT
  - Pooled mITT: this pools data from Phases 1/2/3a/3b and will include evaluations up to Day 92 only
- **Per-Protocol (PP) analysis Set:** Includes all eligible randomized participants who received all protocol-required doses of study vaccine (ARCT-154 or placebo) up to the evaluation timepoint concerned and within the protocol predefined window, and who have no major protocol deviations expected to affect efficacy (PP efficacy), immunogenicity (PP immunogenicity), safety or reactogenicity assessments as determined by the Sponsor Medical Monitor or designee in a blinded manner. The PP analysis set will be analyzed according to which study vaccine was assigned, in the event there is a discrepancy. PP sets will be further derived for efficacy and immunogenicity as follows:
  - **Efficacy**
    - Phase 3b PP efficacy set: includes per protocol Phase 1 participants and excludes any participant with evidence of SARS-CoV-infection on Day 1 up to 7 days after the 2nd study vaccination (IcEv3) or that receives an non-study COVID-19 vaccine prior to Day 92 (IcEv2).
    - Pooled PP efficacy set: includes per protocol Phase 1, 2, 3a and Phase 3b participants and excludes any participant with evidence of SARS-CoV-infection on Day 1 up to 7 days after the 2nd study vaccination (IcEv3) or that receives an non-study COVID-19 vaccine prior to Day 92 (IcEv2).
  - **Immunogenicity**
    - Phase 1 PP immunogenicity set: includes per protocol Phase 1 participants and excludes any participant with evidence of SARS-CoV-2 infection on Day 1 up to Day 57 (IcEv3) or who receives a non-study COVID-19 vaccine prior to the analysis time point concerned (IcEv2).
    - Phase 2/3a PP immunogenicity set: includes per protocol Phase 2 and Phase 3a participants and excludes any participant with evidence of SARS-CoV-2 infection on Day 1 up to Day 57 (IcEv3) or who receives a

non-study COVID-19 vaccine prior to the analysis time point concerned (IcEv2).

- Phase 1/2/3a PP immunogenicity set (or Phase 1/2 PP immunogenicity set): includes per protocol participants from Phase 1, 2 and Phase 3a participants and excludes any participant with evidence of SARS-CoV-2 infection on Day 1 up to Day 57 (IcEv3) or who receives an non-study COVID-19 vaccine prior to the analysis time point concerned (IcEv2). This set will include evaluations of immunogenicity up to Day 92 only. Of note, this analysis set will be restricted to Phase 1/2 participants for analysis of parameters not collected in phase 3a participants and will be referred to as Phase 1/2 PP immunogenicity set)

PP immunogenicity sets will be derived up to the analysis time point concerned based on the availability of each assay. Three time points are considered:

- Up to Day 57
- Up to Day 92
- Up to Day 120

The following major protocol deviations are expected to affect efficacy and will lead to exclusion of a participant from the PP efficacy set:

- Received wrong study vaccine up to Day 92
- Did not receive study vaccine
- Received non-study COVID-19 vaccine (IcEv2) up to Day 92
- COVID-19 infection (positive RT-PCR or other COVID-19 test) up to Day 36
- Result of SARS-CoV-2 anti-nucleocapsid antibodies test is Positive/Undetermined up to Day 36

The following major protocol deviations are expected to affect immunogenicity and will lead to exclusion of a participant from the PP immunogenicity sets:

- Received wrong study vaccine up to the time point concerned
- Did not receive study vaccine
- Received non-study COVID-19 vaccine (IcEv2) up to the time point concerned
- Received confounding medication (IcEv5) up to the time point concerned
- COVID-19 infection (positive RT-PCR or other COVID-19 test) up to Day 57
- Result of SARS-CoV-2 anti-nucleocapsid antibodies test is Positive/Undetermined up to Day 57

All major protocol deviations listed above are conditions leading to exclusion from the PP set specified in the protocol.

- **Immunogenicity Analysis Set (IAS):** Includes all participants who received all protocol-required doses of study vaccine (ARCT-154 or placebo) up to the evaluation timepoint concerned, who have no evidence of prior SARS-CoV-2 infection (no positive RT-PCR or other COVID-19 test or seropositivity for anti-nucleocapsid antibody) up to Day 57 and who have at least 1 valid post-vaccination immunogenicity assay result.

All participants in the IAS will be analyzed according to which study vaccine was assigned.

IAS are defined for the following Phases of the study:

- Phase 1 IAS: this corresponds to data from participants in Phase 1
- Phase 2/3a IAS: this pools data from participants in Phase 2 and 3a
- Phase 1/2/3a IAS (or phase 1/2 IAS): this pools data from Phase 1, 2 and 3a participants and will include evaluations of immunogenicity up to Day 92 only. Of note, this analysis set may be restricted to Phase 1 and Phase 2 participants for analyses on parameters not collected for phase 3a participants.
- **Safety Analysis Set (SAS):** Includes all participants who receive any dose of study vaccine (ARCT-154 or placebo or ChAdOx1). Participants will be analyzed according to the study vaccine received. SAS analysis sets are defined for each Phase of the study as follows:
  - Phase 1/2/3a SAS: this pools data from Phase 1, Phase 2 and Phase 3a participants
  - Phase 3b SAS
  - Phase 3c SAS
  - Pooled SAS: this pools data from Phase 1/2/3a/3b for ARCT-154 and placebo, respectively. It will include evaluations up to Day 92 only (except for unsolicited events)
- **Reactogenicity Analysis Set (RAS):** Includes all participants who receive any dose of study vaccine (ARCT-154 or placebo or ChAdOx1) and provide at least 1 reactogenicity diary report. Participants will be analyzed according to the vaccine received.  
Reactogenicity analysis sets are defined for each Phase of the study as follows:
  - Phase 1/2/3a RAS: this pools data from Phase 1, Phase 2 and Phase 3a participants
  - Phase 2/3a RAS
  - Phase 3b RAS
  - Phase 3c RAS
  - Pooled RAS: this pools data from Phase 1/2/3a/3b for ARCT-154 and placebo, respectively.

For safety analysis sets, SAS and RAS, where participants will be analyzed according to the study vaccine received, in case a participant receives incorrect study vaccine, only data up to the receipt of the incorrect study vaccine (exclusive) will be used in the summaries. If the first dose of vaccine the participant received was the incorrectly assigned one, then only data up to the second dose (exclusive) will be used in the summaries. Outputs for “any dose” that analyze data after any ARCT-154 dose or after any Placebo or ChAdOx1 dose, will include all data after each dose even if participant received an incorrect study vaccine.

Separate listings of safety and immunogenicity data, that are currently planned in this SAP, will be produced for participants receiving at least one incorrect dose of study vaccine. Of note, participants with missing dosing will not be considered as receiving incorrect dosing.

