- Phase 3b PP set: this excludes any participant with evidence of SARS-CoV-2 infection on Day 1 or up to 7 days after the 2nd study vaccination (IcEv3) or that receives an off-study COVID-19 vaccine prior to Day 92 (IcEv2)
- Phase 3c-1 PP set: this includes just the participants enrolled in the Phase 3c-1 subset of Phase 3c but excludes any participant that has evidence of SARS-CoV-2 infection at baseline or prior to the analysis time point concerned (IcEv3) or that receives an off-study COVID-19 vaccine prior to the analysis time point concerned (IcEv2).
- Phase 3c PP set: this includes all of Phase 3c but excludes any participant that has evidence of SARS-CoV-2 infection at baseline or prior to the analysis time point concerned (IcEv3) or that receives an off-study COVID-19 vaccine prior to the analysis time point concerned (IcEv2).
- Pooled PP set: this pools data from Phase 1/2/3a/3b and excludes any participant with evidence of SARS-CoV-2 infection on Day 1 or up to 7 days after the 2nd study vaccination (IcEv3) or that receives an off-study COVID-19 vaccine prior to Day 92 (IcEv2). This will include evaluations up to Day 92 only.

Immunogenicity Analysis Set (IAS): Includes all participants who received all protocol-required doses of study vaccine (ARCT-154 or placebo or ChAdOx1) up to the evaluation timepoint concerned, who have no evidence of prior SARS-CoV-2 infection at Day 1 (IcEv3; Section 8.3.1) and who have at least 1 valid post-vaccination immunogenicity assay result. Data at timepoints following evidence of a SARSCoV2 infection (IcEv3), use of immune-modifying drugs, blood products or immunoglobulins (IcEv5) or non-study COVID-19 vaccines (IcEv2), or protocol deviations (eg, time windows for doses and blood draws for the time period summarized) that may impact immunogenicity as determined by the Sponsor Medical Monitor or designee in a blinded manner will be excluded. All participants in the IAS will be analyzed according to which study vaccine was received. IAS are defined for the following Phases of the study:

- Phase 1 IAS
- Phase 2/3a IAS: this pools data from participants in Phase 2 and 3a
- Phase 1/2/3a IAS: this pools data from Phase 1, 2 and 3a participants and will include evaluations of immunogenicity up to Day 92 only
- Phase 3b IAS
- Phase 3c-1 IAS

8.3 Statistical Considerations for Phase 3

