8.3.1 Estimands and Intercurrent Events for Phase 1/2/3a, Phase 3b and Phase 3c

Possible intercurrent events (IcEvs) are presented in [Table 14](#).

Table 14 Intercurrent Event Types

Label	Intercurrent Event Type
IcEv1 (Death not due to COVID-19)	Death due to any cause other than COVID-19 associated.
IcEv2 (Non-study COVID-19 vaccine)	Use of non-study COVID-19 vaccine.
IcEv3 (Early infection)	Positive RT-PCR test or seropositivity for antinucleocapsid antibody or neutralizing antibody (as assessed by sVNT for Phase 1/2/3a and MNT for Phase 3c) indicating exposure to SARS-CoV-2 prior to vaccination or SARS-CoV-2 infection prior to 7 days (inclusive) after the second study vaccination dose (Day 35). Note: for immunogenicity endpoints, Day 57 is the watershed for early infection.
IcEv4 (Study infection)	Develops virologically confirmed SARS-CoV-2 infection, with or without COVID-19 symptoms more than 7 days after second study vaccine dose (\geq Day 36).
IcEv5 (Confounding On-study Medications)	Receives any of the following concomitant medications/vaccines prior to the time point for which the analysis is being performed: 
• Live vaccines within 28 days before or after any study vaccination• Systemic (oral, intravenous, intramuscular or subcutaneous) corticosteroids given at any study time point prior to the timepoint at which the analysis is being performed• Blood products or immunoglobulins given at any study time point prior to the timepoint at which the analysis is being performed• Immunosuppressive medications, including cytotoxic medication for cancer or autoimmune disease, given at any study time point prior to the timepoint at which the analysis is being performed

Abbreviations: COVID-19=coronavirus disease 2019; IcEv=intercurrent event; SARS-CoV-2=severe acute respiratory syndrome coronavirus 2

Attributes for the principal safety and immunogenicity estimands for Phase 1/2/3a, 3b and 3c with strategies for IcEvs are presented in the tables below.

Table 15 Estimands for Phase 1/2/3a Substudy and Phase 3c Substudy Primary, Secondary and Exploratory Immunogenicity Endpoints

Estimand Label	Estimand 1 (immunogenicity)

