Exploratory 4b	COVID-19 with onset at any time after the first dose of study vaccine administration and up to Day 92	ITT + no prior infection (3b & Pooled)	[Last date at risk – Date received 1st dose]+1	No
Exploratory 5a	Severe COVID-19 with onset between Day 36 and Day 92 by specific variant	miITT (3b & Pooled)	[Last date at risk – Date received 1st dose]+1	No
Exploratory 5b	Severe COVID-19 with onset at any time after the first dose of study vaccine administration and up to Day 92	ITT + no prior infection (3b & Pooled)	[Last date at risk – Date received 1st dose]+1	No

\*COVID-19 events will be confirmed, protocol-defined cases. \*\* Where the last date at risk will be defined as COVID-19-event date or censor date, whichever comes first.

(a) Unless specified otherwise, reference to the protocol endpoints is a reference to the Phase 3b endpoints.

Confirmed, protocol-defined COVID-19 cases will be determined by case report form (CRF) data, as confirmed by the blinded Independent Adjudication Committee and adjudicated for severity, with the date of case onset as date of symptom onset and date of positive COVID test date, whichever occurs first. Both protocol-defined and (protocol-defined) severe cases flagged in the CRF will be included in the primary endpoint.

For participants with no covid-event during the time interval the censor date for the last date at risk is whichever of the following comes first:

- Date of completion of Day 92 visit;
- Date of death unrelated to COVID-19;
- Date of receipt of Switchover or receipt of non-study COVID-19 vaccine
- Lost to Follow-up (last known alive date or date of Day 1+91 days, which is earlier).

Section 9.2.2 presents the endpoints and analyses in terms of estimands for primary, secondary and exploratory efficacy analyses.

As a sensitivity analysis of the primary endpoint (Phase 3b only), severe cases and deaths due to COVID-19 will be repeated using all COVID-19 cases from CRF, including those cases that are not confirmed by the blinded Independent Adjudication Committee and with severe or death severity as reported in the CRF.

Day 36 is defined as second dose+7 days (29+7=36 days), and Day 92 is defined as second dose+63 days (29+63=92 days). Another sensitivity analysis of the primary endpoint (Phase 3b only) will be performed using Day 92 visit instead of second dose+63 days.

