COVID-19 cases confirmed by the blinded Independent Adjudication Committee will be presented as frequency table by time intervals of Day 1-Day 35 and Day 36-Day 92 for RS, ITT, mITT and PP. Severe COVID-19 and death due to COVID-19 by the blinded Independent Adjudication Committee will also be presented.

Number of suspected COVID-19 cases reported from Day 1 to Day 92, those tested with any COVID testing within 14 days after symptoms onset, and Proportion of participants who had COVID testing performed within 14 days after symptoms onset from Day 1 to Day 92 will be presented the Randomized Set.

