#### 6.4.1 Primary Efficacy Analysis

The analysis of the first primary endpoint will consider the first occurrence of confirmed, protocol-defined COVID-19 with onset between Day 36 and Day 92 inclusive.

Time at risk = [Last date at risk – (Date received 2nd dose + 7 days)]+1; where the last date at risk will be defined as COVID-19-event date or censor date, whichever comes first.

Summaries of vaccine efficacy will display the number of participants included in the analysis, number of protocol-defined COVID-19 cases (Protocol Appendix 2) and surveillance time in person-year will be summarized in each vaccine group. Surveillance time refers to the total person-time at risk (years) for the given endpoint.

The vaccine efficacy (VE) is defined as the percent reduction in the hazard rate of the COVID-19 events (ARCT-154 versus placebo). The vaccine efficacy is calculated as:

$$VE = 1 - \frac{h_{ARCT-154}}{h_{placebo}} = 1 - HR$$

where  $h_{ARCT-154}$  and  $h_{placebo}$  are hazard rates of the confirmed, protocol-defined COVID-19/Severe COVID-19/death among those in ARCT-154 group and placebo group, respectively.

Vaccine efficacy will be displayed together with 95% confidence interval (CI). Vaccine efficacy is calculated from 1-hazard ratio, where, the hazard ratio (HR) and 95% CI are measured by adjusted Cox proportional hazard regression, with the assumptions of proportional hazards over time. The p-value will be calculated from Cox proportional hazard regression.

Efficacy summaries will also include the proportion of participants with COVID-19 cases in each vaccine group will be displayed together with the Clopper-Pearson 95% CI and a comparison between ARCT-154 and Placebo with 95% CIs. A Log-Rank test p-value will be calculated (in addition to VE% Cox model p-value).

Factors to be used as covariates in Cox proportional hazard regression include:

- Risk group: A randomization stratification factor for age and health risk for severe disease;  $\geq 18$  to  $< 60$  years and “healthy”,  $\geq 18$  and  $< 60$  years and “at risk” and  $\geq 60$  years. Age and health risk at randomization collected in the CRF will be used.
- Study site region: Study site is a randomization stratification factor. However, the sites are grouped into study site region for adjustment factor. Site collected in the CRF will be used.
  - Risk group or study site region will be removed from the model when performing subgroup analysis on that variable.

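### The Phase 3b per-protocol efficacy set is wrong as written (Phase 1 membership, Day 36 cut-off), and the mITT infection rule widened after unblinding has only partial checks

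*SAP*

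**What the plan says.** **PP efficacy set.** SAP 4.1 begins the definition with "Phase 3b PP efficacy set: includes per protocol Phase 1 participants". The deviations that remove a participant include "COVID-19 infection (positive RT-PCR or other COVID-19 test) up to Day 36", and a positive or undetermined anti-nucleocapsid result up to the same day. The list is followed by: "All major protocol deviations listed above are conditions leading to exclusion from the PP set specified in the protocol".

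Below Table 6 the SAP states: "Day 36 is defined as second dose+7 days (29+7=36 days". The primary endpoint in SAP 6.4.1 is "protocol-defined COVID-19 with onset between Day 36 and Day 92 inclusive". Protocol 8.2 excludes from the Phase 3b PP set anyone with "evidence of SARS-CoV-2 infection on Day 1 or up to 7 days after the 2nd study vaccination (IcEv3", and Protocol 8.3.1 (Table 14) describes that event as "SARS-CoV-2 infection prior to 7 days (inclusive) after the second study vaccination dose (Day 35".

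**mITT infection rule.** SAP 4.1 bars from the mITT anyone positive by RT-PCR, by another COVID-19 test, or for anti-nucleocapsid antibody, at baseline or early in the series. SAP 7.2 shows that SAP Part 2 (6 April 2022) recognised only RT-PCR and anti-nucleocapsid antibody. SAP 7.1, which covers changes not made in SAP Part 1 or Part 2, records the added test and notes that it alters the mITT.

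**Case confirmation.** Protocol Appendix 2 accepts RT-PCR, an equivalent nucleic acid test, or a rapid antigen test. Protocol 7.1.1 requires RT-PCR or equivalent. The primary hypothesis in Protocol 8.5.2 and SAP 6.1 concerns PCR-confirmed disease.

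**The concern.** The PP set is the stricter companion to the overall primary analysis. SAP 6.4.1.1 also repeats the severe-disease and death analyses in it, and SAP 4.2 says the PP exclusions will be re-programmed for the final analysis. The text is therefore a programming instruction. Taken literally, it yields either a set with no Phase 3b participants or one that drops cases the endpoint is meant to count.

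The mITT rule decides who enters the primary analysis. SAP Part 2 preceded the April 2022 unblinded efficacy analysis. The only later plans are the 6-month SAP (Version 1.0 signed in December 2022) and the final SAP (July 2023). SAP 2.4 says that some authors of both had participant-level unblinded data. When a primary-set rule changes in those circumstances, a reader will want the result under the preceding rule, and the plan does not provide it.

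An unresolved case definition leaves open whether an antigen-only case counts.

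**Working it through.** **1. The plan's event count.** Inputs from SAP 6.1: null HR 0.7, true HR 0.5, 1:1 allocation, one-sided 0.025, 372 cases. Schoenfeld power = Φ(√(E/4) × ln(0.7/0.5) − 1.96). With E = 372 this is 0.9006, so the stated 90% reproduces.

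**2. Day arithmetic.** Dose 2 is on Day 29. 29 + 7 = 36, and 29 + 6 = 35. The window from Day 36 to Day 92 is 92 − 36 + 1 = 57 days. An exclusion through Day 36, read inclusively, overlaps the window by one day.

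**3. Which cut-off is intended.** Early infection is labelled Day 35 (Protocol Table 14, SAP Table 5). Secondary endpoint 4 uses Day 1 to Day 35 (SAP 6.4.2.4). The efficacy estimand separates infections before Day 36 (SAP 9.2.2). The case counts are planned as a "frequency table by time intervals of Day 1-Day 35 and Day 36-Day 92 for RS, ITT, mITT and PP". All of these put Day 35 outside the window and Day 36 inside it. The ambiguity starts in the protocol: its PP and mITT wording of 7 days after dose 2, repeated for the mITT in SAP 4.1, reaches Day 36 by the same sum.

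**4. Size of the overlap**, assuming uniform onset and using the planned 372 cases as the scale:
- Cases on Day 36: 372/57 = 6.5. At HR 0.5 they split 2:1, about 4.4 placebo and 2.2 vaccine, so the estimated efficacy does not move.
- Remaining cases: 372 − 6.5 = 365.5, giving power 0.8955.
- Lower 95% limit = 1 − 0.5 × exp(1.96 × √(1/placebo + 1/vaccine)). With 248 and 124 cases it is 37.97%. With 243.6 and 121.8 it is 37.85%.
- If the Day 36 hazard is 0.5 to 3 times the average (an assumed range), 3.3 to 19.6 cases are lost and power is 0.898 to 0.885.

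Under uniform onset, 6.5 is a ceiling. The exclusion follows the positive test, whereas onset is the earlier of symptom and test (SAP 6.4), so symptoms on Day 36 with a first positive test later remain in the set. Scheduled Phase 3b anti-nucleocapsid samples fall on Days 1 and 29 (Protocol 4.5.5.3), so that half of the rule should remove almost nobody on Day 36.

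**5. Checks on the mITT rule.** The planned analyses of the primary endpoint are the mITT, the PP set, all CRF-reported cases, the Day 92 visit as end of window, and the pooled sets (SAP 6.2.4, 6.4, 6.4.1.1, 7.1). None uses the SAP Part 2 rule. The documents give no count of participants positive only by another test, so neither size nor direction can be computed.

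**6. Carry-through.** For secondary endpoint 2, SAP Table 2 excludes prior infection by three criteria (RT-PCR, other test, anti-nucleocapsid), while SAP 6.4.2.2 lists two, omitting the other test. Exploratory endpoints 1 and 2 show the same split between Table 2 and SAP 6.4.3.1 and 6.4.3.2.

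**The case against.** **On the PP set.** The reference to Phase 1 is an obvious copying slip in a line headed Phase 3b, and the Day 36 cut-off follows the protocol's own 7-day wording. Both points stand as explanations, but the text still needs correcting. The sentence after the list can also be read as describing the PP set and not as claiming that the list matches the protocol, so it should not be called a misstatement. A reader might infer that the overlap distorts the primary result. It does not: it concerns a sensitivity set, applies equally to both arms, and the intended mITT cut-off is clear from the day labels.

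**On the mITT rule.** The change is logged with a reason, and Protocol 8.2 does not restrict the type of test. SAP 2.4 states that unblinded access was not thought to have influenced the plan. Partial checks exist: exclusion reasons by arm (SAP 4.2), case tables by analysis set (SAP 6.4), secondary endpoint 4 and Exploratory 3. None is an exact re-run, because secondary endpoint 4 admits baseline seropositives and Exploratory 3 uses a different population and window. The April 2022 result is no substitute, since SAP 2.5 says that analysis departed from SAP Part 2 in places. A reader might infer that the rule was widened to improve the result; nothing in the documents shows that.

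**On secondary endpoint 2.** The split might look like a threat to the testing hierarchy. It concerns infection before Day 1, and exclusion criterion 3 already removes known COVID-19 and RT-PCR positives, so few participants should be affected.

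**On antigen tests.** The Amendment 8 log records that antigen-based efficacy analyses were removed, so the Appendix 2 phrase is probably leftover. It also mentions over 400 PCR-confirmed cases under adjudication, which suggests that antigen-only cases are few.

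**Conclusion.** The PP efficacy definition is wrong as written, in membership and in cut-off day. The cut-off costs at most about 6.5 of 372 cases under uniform onset, with efficacy unchanged, power 0.895 against 0.901, and a lower limit about 0.1 percentage point lower. This assumes inclusive reading of the Day 36 limit, the planned 50% efficacy and proportional hazards.

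The missing re-run on the SAP Part 2 mITT is a gap in transparency, not evidence of bias. The widening is disclosed and compatible with the protocol; its effect is unknown and only partly visible in the planned tables. The split prior-infection wording and the antigen phrase are reconciliation points that probably concern few participants. None of this shows the primary result to be wrong. The corrections are worth making because they are specific and cheap.

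**What to change.** - **PP set.** In SAP 4.1, define the Phase 3b PP efficacy set from Phase 3b participants and end its infection and anti-nucleocapsid exclusions at Day 35. Align the 7-day wording in the mITT definition and in SAP Table 5 with the Day 35/Day 36 split.
- **mITT.** Add one sensitivity analysis of the Phase 3b primary vaccine efficacy on the SAP Part 2 mITT (RT-PCR or anti-nucleocapsid). Report by arm the participants and cases that differ. State one prior-infection rule for secondary endpoint 2 and Exploratory 1 and 2 in both SAP Table 2 and SAP 6.4.
- **Case confirmation.** Reconcile Appendix 2 with Protocol 7.1.1 and the PCR-confirmed hypothesis. Report any adjudicated antigen-only cases by arm, with a sensitivity analysis that excludes them. Do not remove them from the primary count now, because that would itself change the endpoint after unblinding.

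The cost is wording edits, the re-run from data already held and, if antigen-only cases exist, one more sensitivity analysis. The downsides are a second mITT version to explain and edits made after unblinding. Those edits should be logged in SAP Section 7 with counts by arm.
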